Title: High flow nasal cannula compared to continuous positive airway pressure in the treatment of obstructive sleep apnea

Investigator: [name]

Official Title: Director of Sleep Center

NCT number: NCT03843372

Document date: June 08, 2020

Materials and Methods

This work was approved by the institutional review board of Chang Gung Memorial Hospital (201601844B0C101), and all subjects signed informed consent forms in accordance with the amended Declaration of Helsinki. Subjects who were diagnosed with OSAHS via standard polysomnography (PSG) were recruited in the sleep center of Chang Gung Memorial Hospital. The definition of OSAHS was an AHI greater than 5 times per hour (times/hr). Patients with central sleep apnea, hypoventilation syndrome, chronic obstructive airway disease, an unstable hemodynamic state, who were younger than 18 years old, with an Eastern Cooperative Oncology Group Performance Status higher than grade 2, who experienced intolerance to HFNC or CPAP, and pregnant women were excluded. In addition, patients who recently underwent surgery or used an oral appliance were also excluded.

Study Protocols

This was a prospective crossover study. All of the participants were randomized into two groups for minimized first night effects. All of them would receive one-night HFNC therapy and another night for CPAP titration under PSG monitoring. The duration between these two treatments was approximately one week apart. The first group underwent CPAP titration on the first night and HFNC titration on the second night. Conversely, the second group was subjected to HFNC on the first night and CPAP titration on the second night. All of the participants were asked and recorded their side effects following completion of an HFNC or CPAP.

Polysomnography and scoring methods

Standard overnight PSG included recording electroencephalography, bilateral electroculograms, submental electromyogram, electrocardiography, nasal pressure, oronasal thermistor, oximetry, chest, and abdominal movement (inductance plethysmography), body position, sound intensity, and bilateral tibia electromyogram. All signal results for each night were collected and digitized on a computerized PSG system (Embla N7000, USA; Compumedics, Australia). Sleep stages and respiratory events were scored according to the American Academy of Sleep Medicine (AASM, Version 2.4; 2017) scoring manual.

CPAP titration

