The most of respiratory event and sleep quality parameters were not normal distribution. Therefore, the carry over effect of CPAP and HFNC were evaluated by Wilcoxon rank sum test. The AHI, desaturation index, sleep efficiency, and total sleep time between CPAP titration, and HFNC were also compared with the Wilcoxon rank sum test. The side effects of HFNC and CPAP were compared with the chi-square test and Fisher's exact probability test. A p-value < 0.05 was considered statistically significant. Statistical evaluations were performed using the SPSS 16.0 Software (SPSS Inc., Chicago, Ill). Data were presented as median \pm interquartile range (IQR). P-values < 0.05 were considered to be statistically significant.

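### Several device comparisons are each judged at p < 0.05, with no primary outcome and no multiplicity control, so nothing says which result answers the trial's question

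*Combined protocol and SAP*

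**What the plan says.** Everything on this point is in the Statistical analysis section. The efficacy comparison reads: "The AHI, desaturation index, sleep efficiency, and total sleep time between CPAP titration, and HFNC were also compared with the Wilcoxon rank sum test". Side effects are handled separately: "The side effects of HFNC and CPAP were compared with the chi-square test and Fisher's exact probability test". The decision rule is given once as "A p-value < 0.05 was considered statistically significant" and repeated at the end of the paragraph as "P-values < 0.05 were considered to be statistically significant".

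The document names no primary outcome, hierarchy, multiplicity adjustment, sample size, power or familywise error rate. It does not say whether tests are one- or two-sided, or how many side-effect items are compared. The section also contains a carry-over test ("the carry over effect of CPAP and HFNC were evaluated by Wilcoxon rank sum test"). That is not a device comparison, so it is not counted here.

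Two other sections bear on the point. Study Protocols states the design: "This was a prospective crossover study", with each patient receiving both devices. High flow titration defines the optimal flow by two criteria together, the AHI achieved and whether sleep is maintained. AHI therefore guides the titration, but the document does not call it the trial's main outcome.

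**The concern.** With one threshold applied to several unranked outcomes, the plan lets a significant result on any of them stand as a device difference. This has two consequences.

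- **Error rate.** When several tests are each run at 5%, the chance that at least one gives a false positive is above 5%, and no outcome is singled out to carry the conclusion.
- **Interpretation.** The two breathing outcomes and the two sleep outcomes can point in opposite directions. HFNC might give better sleep and a worse AHI, for example. The plan has no rule for which result answers the question, so a report could lead with either. This problem remains whatever the exact error rate.

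**Working it through.** The plan states no familywise figure, so there is none to reproduce. The calculation starts from its threshold and its list of comparisons.

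**Inputs from the Statistical analysis section.** Per-test level 0.05 (two-sided assumed); four efficacy comparisons; at least one side-effect comparison.

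**Inputs that are assumptions.** Correlations between outcomes, correlation between a patient's two nights, and 30 patients in one simulation. The document gives none of these.

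**Step 1: independent tests, true size 5%, no real difference on any outcome.** The chance of at least one false positive among k tests is 1 - 0.95^k.
- Four efficacy tests: 1 - 0.95^4 = 18.5%.
- Four plus one side-effect test: 1 - 0.95^5 = 22.6%.
- Eight tests, if side effects were tested as four items: 1 - 0.95^8 = 33.7%. The item count is unknown, so this is illustration only.

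**Step 2: correlated outcomes.** Simulated jointly normal test statistics, two-sided 0.05, all nulls true. First, the outcomes are paired as breathing (AHI with desaturation index) and sleep (total sleep time with sleep efficiency):

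| Correlation within pair | Across pairs | Four-test rate |
|---|---|---|
| 0.5 | 0.2 | 17% |
| 0.8 | 0.2 | 15% |
| 0.8 | 0.3 | 15% |
| 0.9 | 0.3 | 13% |

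Adding one independent side-effect test, with within-pair correlation 0.7-0.9, gives about 17.6-20.2%. If instead all four outcomes share one common correlation, the four-test rate is 17.4% at 0.3, 15.6% at 0.5, 13.1% at 0.7, 11.4% at 0.8 and 9.4% at 0.9.

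**Step 3: if some outcomes truly differ.** Only the remaining null outcomes can produce false claims. If AHI alone differs: 1 - 0.95^3 = 14.3%. If both breathing outcomes differ: 1 - 0.95^2 = 9.75%. Both take the remaining tests as independent.

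**Step 4: the test as written.** The rank-sum test treats the two nights as independent samples. With within-patient correlation rho, the variance of its standardised statistic is roughly 1 - rho, so the true size is about 2 × [1 - Phi(1.96 / sqrt(1 - rho))].

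| rho | Size per test | Four independent outcomes, 1 - (1 - size)^4 |
|---|---|---|
| 0.2 | 2.8% | 10.9% |
| 0.3 | 1.9% | 7.4% |
| 0.5 | 0.6% | 2.2% |

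Simulating the rank-sum test itself with 30 patients gave per-test sizes of 2.0% at rho 0.3 and 0.7% at rho 0.5, close to the approximation.

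**Step 5: after the fix.** One primary outcome tested by a valid paired method has an error rate of 5%. For comparison, Bonferroni at 0.05 / 4 = 0.0125 across the four efficacy outcomes gives 1 - 0.9875^4 = 4.9% if they are independent.

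**The case against.** A reader might infer that the plan as it stands carries a false-claim rate of about 13-19% where 5% was promised. The documents do not support that reading, for four reasons.

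- The plan promises no 5% familywise rate. It states a per-test threshold only.
- The range needs correctly sized tests, and the plan names an unpaired test for crossover data. With positively correlated nights that test is conservative, and Step 4 shows the familywise rate can drop below 5%.
- The range covers only the four efficacy tests and rests on assumed correlations. Side-effect tests raise it; a strong common correlation lowers it to about 9-11%.
- It requires that no outcome truly differs, although a real difference in breathing outcomes is plausible.

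All four limits stand. They restrict the number, not the defect. An unsuitable test that happens to be conservative is not multiplicity control, and correcting it alone would bring the inflation in Steps 1 and 2 into play.

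It can also be argued that a small comparative study may test each outcome on its own terms, with all four named in the plan and AHI listed first. That is a recognised approach, so strict familywise control is partly a matter of choice. But being listed first is not a designation, and the approach still does not say which outcome decides when they conflict.

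A second tempting inference is that AHI is already primary because it steers the titration. High flow titration pairs it with maintained sleep, and CPAP titration uses a wider set of targets. This supports choosing AHI but does not show that the choice was made.

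**Conclusion.** The concern holds in a limited form. The absence of a primary outcome, a ranking and an adjustment is plain in the text. It lets the trial claim a device difference on whichever outcome crosses 0.05, and leaves conflicting results unresolved.

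The size is conditional. With all nulls true and valid 5% tests, it is at most 18.5% for four tests and 22.6% for five (the independent case), and about 13-17% for the four under the paired correlations assumed above. For the plan run literally, with the unpaired test, it is lower and possibly under 5%. No single percentage should be quoted as the plan's error rate. The case for a change rests mainly on the missing primary outcome, and the percentages show what would follow once the test is corrected.

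**What to change.** State in the Statistical analysis section that the within-patient HFNC-CPAP difference in AHI is the single primary outcome, tested two-sided at 0.05 with a paired method suited to the crossover. Label the desaturation index, both sleep outcomes and the side effects as secondary. Then choose one of two routes for them: report them with 95% CIs as supportive, or, if significance is to be claimed, adjust for multiplicity, for example by Holm. Whether to make secondary claims conditional on a significant AHI result is the sponsor's choice and should be stated.

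The section is written in the past tense and describes the distribution of the outcomes, which suggests that data may have been examined. If they had been, the choice of primary outcome should be disclosed as post hoc; it would clarify the report but could not restore prespecified error control.

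The cost is a few sentences and no new data. AHI keeps its full 0.05. Adjusted secondary claims lose power. With Holm over the three secondary efficacy outcomes, the first step needs p < 0.05 / 3 = 0.0167, so power of 80% at 0.05 falls to Phi(1.960 + 0.842 - 2.394) = 66%. If those claims are also conditional on AHI, and AHI has 80% power and is independent (assumed), that becomes 0.80 × 0.66 = 53%. A gate of this kind would also rule out a sleep claim when AHI is similar on the two devices.

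### Each HFNC–CPAP comparison yields only a p-value, with no within-patient effect estimate or confidence interval; the median ± IQR format is a lesser, conditional reporting flaw

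*Combined protocol and SAP*

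**What the plan says.** All of this is in the combined protocol and SAP.

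- Study Protocols sets the design: "This was a prospective crossover study". Each participant has one HFNC night and one CPAP night about a week apart, in randomised order.
- Statistical analysis opens with a statement about distributions: "The most of respiratory event and sleep quality parameters were not normal distribution".
- AHI, desaturation index, sleep efficiency and total sleep time on the two devices "were also compared with the Wilcoxon rank sum test".
- The criterion is "A p-value < 0.05 was considered statistically significant", given twice in the section. Whether the test is one- or two-sided is not stated.
- On presentation: "Data were presented as median", followed by a plus-or-minus sign and the interquartile range.

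No section mentions an estimate of the device difference or a confidence interval for it.

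**The concern.** The title promises a comparison of two treatments, and a reader will want to know how far apart they are and how precisely that is known. The planned output is two per-device summaries and a p-value. The summaries describe spread between patients. They do not show the precision of the difference within patients, which is what a crossover is run to measure.

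The stake is interpretation in both directions. A non-significant AHI result could be read as equivalence when the data also allow HFNC to be much worse. A significant one would come without a size.

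The presentation format adds a smaller problem. The IQR is one distance, Q3 − Q1. Placing it on both sides of the median makes a symmetric band two IQRs wide, which is neither the quartiles nor a confidence interval. It hides the skew that led the plan to rank methods. AHI cannot fall below 0 and sleep efficiency cannot exceed 100%, yet such a band can do either.

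**Working it through.** The plan states no sample size, power, on-treatment AHI or spread, so there is no planned figure to reproduce. The only AHI value is the diagnostic threshold in Materials and Methods: "The definition of OSAHS was an AHI greater than 5 times per hour". Every distribution below is therefore an assumption.

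**1. What a p-value alone leaves open.** Take an approximately normal estimate d with standard error s and a two-sided test. The p-value fixes only the ratio d/s. At p = 0.05, |d| = 1.96s, and the 95% interval d ± 1.96s runs from 0 to 2d. If d is 1 event/hr the interval is 0 to 2; if d is 10 events/hr it is 0 to 20. The p-value is the same and the clinical message is not. (Both values of d are arbitrary.)

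**2. Share of patients inside median ± IQR.** For normal data, IQR = 2 × 0.6745 SD = 1.349 SD, so the share is 2Φ(1.349) − 1 = 82.3%. For other shapes it is F(median + IQR) − F(median − IQR):

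| Assumed shape | Share inside |
|---|---|
| Log-normal, log SD 0.25 / 0.5 / 1 / 2 | 83.0% / 84.2% / 81.5% / 77.7% |
| Exponential | 83.3% |
| Gamma, shape 0.5 to 4 | 80.5% to 85.4% |
| t, 2 to 5 df | 75.6% to 79.4% |

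These run from about 76% to 85%. Left-skewed beta shapes, a rough stand-in for sleep efficiency, come out slightly higher at 85.5% to 86.6%, and a uniform distribution is covered entirely. The quartiles enclose 50% by definition.

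**3. When the lower limit is negative.** This happens when IQR > median. For a log-normal, IQR/median = 2 sinh(0.6745σ), which exceeds 1 when σ > asinh(0.5)/0.6745 = 0.713, equivalent to Q3/Q1 above about 2.6.

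- Median 7.39, σ = 1: quartiles 3.8 and 14.5, IQR 10.74; 7.39 ± 10.74 = −3.35 to 18.13.
- Median 10, σ = 0.8: IQR 11.3; −1.3 to 21.3.
- Median 30, σ = 0.5: IQR 20.6; 9.4 to 50.6, so no impossible value.

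**4. The upper bound for sleep efficiency.** With assumed quartiles of 72% and 92% and median 85%, the IQR is 20 points and the band is 65% to 105%.

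**The case against.** The strongest reply concerns the format. The median and the IQR are the right statistics for skewed data, and the ± sign may be loose shorthand for the pair, with no subtraction intended. A table entry of 7.4 ± 10.7 prints no impossible number. The notation changes neither the test nor its type I error. All of that stands, and it is why the format is secondary here. Even on the loose reading, though, a single IQR width does not let a reader recover Q1 and Q3 of a skewed variable.

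A reader might go further and infer that the trial's error bars will run below zero AHI and span about 82% of patients. The documents do not support that. They mention no error bars and give no on-treatment AHI, and the median 30 example shows that a negative limit is not inevitable. The figure of 82% is the normal-distribution value, for the distribution that the plan says mostly does not apply. A negative limit is plausible, because both titration procedures aim to drive events towards zero, but it is conditional.

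Against the main point, it can be said that a reader could subtract the two reported medians. That gives no interval, and for skewed data a difference of medians is not in general the median within-patient difference.

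A fair criticism of the remedy also stands. Quartiles per device still describe only between-patient spread, and a paired interval printed beside an unpaired rank sum p-value could contradict it. The test has to change with the estimate.

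**Conclusion.** The point holds, with the missing estimate and interval as its substance. That part rests on the text alone: no effect size or interval is planned for any of the four measures, in a design where each patient yields a paired difference. Its consequence cannot be quantified from these documents.

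The format point holds in conditional form. Read literally, median ± IQR covers roughly 76% to 85% of patients under the assumed log-normal, exponential, gamma and t shapes (slightly more under the beta shapes), and it gives a negative AHI limit only if the IQR exceeds the median. It would be wrong to infer from the format that the significance test is invalid.

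The change is worth making because, without it, the trial does not quantify its own comparison.

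**What to change.** Replace the presentation sentence and add an estimation sentence, for example:

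> Data are presented as median (25th percentile, 75th percentile) by device and sequence group. For AHI, desaturation index, sleep efficiency and total sleep time, the treatment effect is the Hodges-Lehmann estimate of the within-patient difference, HFNC minus CPAP, with its 95% confidence interval.

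State one matching test, and use it in place of the rank sum comparison of the two devices:

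- the Wilcoxon signed-rank test on the within-patient differences, with the Hodges-Lehmann estimate from the same differences; or
- to allow for period, the rank sum test comparing within-patient period differences (night 1 minus night 2) between the sequence groups. Taking the HFNC-first group minus the CPAP-first group, the location shift is twice the HFNC−CPAP effect, so the Hodges-Lehmann shift and its limits are halved.

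The second fits the plan's own concern with first-night effects. Whichever is chosen, estimate, interval and p-value should come from the same analysis, and the choice should not depend on the results.

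The cost is a small amount of extra analysis and revised table shells. All inputs come from the two nights already recorded, and no study procedure changes. The analyst should confirm that the named SPSS release produces the interval; if it does not, it can be computed from the patient-level differences.
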